7.2 Investigations

The following samples for laboratory assessments need to be taken for a combination of main trial assessments and mechanistic studies.

7.2.1 Laboratory assessments

7.2.1.1 Blood Sample Collection (as per [study schedule 7.1](#))

Blood samples (10 mls EDTA and 9 mls for Transfix) will be taken at intubation start as screening evaluation, then 24h after last treatment for poractant alfa group and 72h after randomization for control group. Then at Day 28 or at ICU discharge whichever occurs earlier. In particular:

- *Laboratory analysis*: blood count, bilirubin, creatinine, eGFR, glucose, AST, ALT, LDH, D-dimer, CRP, procalcitonin
- *Arterial blood gas (ABG) analyses*: approximately (~1 ml) of blood sample for the analysis of pH, pCO₂, pO₂, HCO₃, lactate will be taken at screening, before randomisation and 6,12, 24h after each administration up to 72 hours for poractant alfa group; before randomisation and at 6, 12, 24, 30, 36, 48, 54, 60, 72h after randomisation for control group. Then every 24 hours until day 28 or ICU discharge whichever occurs earlier
- *Mechanistic blood laboratory analysis*: inflammatory indices such as cellular and cytokine inflammatory markers and lipid mediators before randomisation and 12, 24, 48, 72, 96h after first administration (while hospitalised) and relative timepoints in the control group since randomization. These analyses are planned only in the UK subpopulation

7.2.1.2 Urine pregnancy test

Urine will be tested for β HCG at screening for female of childbearing potential. As patients will not have the capacity to confirm their medical history in relation to their childbearing potential and this information may not be available in their medical notes, investigator discretion will be used to confirm whether pregnancy testing is required.

7.2.2 Closed suction tracheal aspirate (TA) samples

Closed suction tracheal aspirate (TA) samples will be taken before the first surfactant dose and after 12, 24, 48, 72, 96h and relative timepoints in the control group since randomisation.

The subsequent samples will be used for the mechanistic studies outlined above ([section 2](#)) and will assess the efficacy of surfactant administration.

The TA samples will consist of blind suctioning by a cannula introduced through a port into the endotracheal tube. A volume of 20-50 ml saline will be administered, with an estimated recovery of 8-10 ml. This procedure will not interrupt the ventilator circuit and will not result in desaturation.

Clinical Study Code No.: CLI-050000-04	Version No.: 4.0
EUDRACT No.: 2020-002632-75 – IND No: 153286	Date: 02 MAR 2021

Blind suctioning following the administration of small volumes of saline is routine practice for the clearance of secretions in ventilated patients.

7.2.3 Laboratories involved

The above-mentioned analysis is a part of the standard care for these patients and will be carried out by local hospital laboratories. Specific assessments concerning to the mechanistic investigations will be performed at the University College London laboratory and at Imperial College, London.

The sample collection, processing storage and shipment for analysis will be described in a laboratory manual.

These exploratory parameters will be assessed only on UK patients enrolled in the study. Given the current pandemic situation and the samples delivery procedure within 48h, it has been deemed appropriate to avoid additional burden for American sites.

Surfactant lipid composition and concentration (University College London)

Mass spectrometric analysis of molecular species compositions of phosphatidylcholine (PC), sphingomyelin (SM), phosphatidylglycerol (PG) and phosphatidylinositol (PI) in small volume BAL samples. It would be expected a reduced surfactant concentration and altered composition in baseline samples taken immediately before surfactant administration. These would both change after surfactant is given, and the aim is to assess the ratio of exogenous to endogenous surfactant from these two different compositions [31][32].

Analysis of sequential samples will provide an indication of exogenous surfactant turnover. Liquid Chromatography with Mass spectrometric analyses will also be performed to establish corresponding lipidomic profiles of matching plasma and airway samples, that will include analyses of related lipid species and lipid derived inflammatory mediators.

Surfactant function (Imperial College, London)

Surfactant function will be determined by measuring surfactant adsorption to the air: liquid interface in a Langmuir trough. The tensioactive properties of lung surfactant from patients' BAL will be measured. It will be investigated whether isolated surfactant will have compromised function by the inhibition of plasma proteins, and whether the function can be recovered after administration of supplemented surfactant. Maximum reduction of the surface tension over continuous compression: expansion cycles models the physiological breathing cycles of intubated patients and will be carried out on a captive bubble surfactometer or similar device. Adsorption analysis of the equilibrium surface tension, together with kinetics of the process, will explore inhibition processes in surfactant function.

Immunological and inflammatory assessment (University College London)

Immune cellular components will be profiled to depth and soluble fluids for soluble mediators including those that imply a bacterial or fungal co-infection. The volume needed would depend on the concentration of the cellular component. Fixed blood will be split into 3 and then to each, a cocktail of antibodies will be added to enumerate all T cell subsets and markers of their subtype and activation. B cell subsets and their antibody isotype will also be investigated. The proportions of cells identified will be compared to normal ranges within each age group. We will be specifically looking at the neutrophil to lymphocyte ratio that is described to be inverted in patients with the disease. Mast cell activation may play an important role in the adverse host response and this will be assessed by the measurement of lipid mediators such as leukotrienes and prostaglandins in airway samples and blood. Multiplex cytokine analysis on tracheal aspirates and blood will characterize the impact of surfactant therapy on the inflammatory cytokine storm.

Clinical Study Code No.: CLI-050000-04	Version No.: 4.0
EUDRACT No.: 2020-002632-75 – IND No: 153286	Date: 02 MAR 2021

The level of the immunomodulatory surfactant protein D (SP-D) in serum has shown to be a promising biomarker for lung inflammation (and hence low levels in BAL), and we will quantify the level of SP-D in both BAL and plasma using our established ELISA. We will also quantify the level of C-reactive protein in BAL as a biomarker for blood contamination of surfactant together with total protein concentration. We have seen that an inflammatory response to infections can result in specific degradation dependent on the infectious agent. We will analyse the degradation of SP-D and its sister protein SP-A using SDS-PAGE and Western Blot analysis to evaluate if COVID-19 infection results in degradation.

8. EFFICACY ASSESSMENTS

Primary Endpoint

The primary outcome variable will be the number of days alive and ventilator-free defined as the number of days the patient is alive and not receiving mechanical ventilation over the **21 days** following randomisation.

Mechanical ventilation will be defined as invasive and non-invasive. Patient will be defined free of mechanical ventilation after 12 hours from the suspension of either invasive and non-invasive ventilation. Patients who die or are mechanically ventilated longer than this period are assessed as zero ventilator-free days.

Key secondary endpoint

- Percentage of patients alive and free of respiratory failure (i.e., need for mechanical ventilation, ECMO, non-invasive ventilation, or high-flow nasal cannula oxygen delivery) at **Day 28**

Secondary endpoints

- Number of days alive and ventilator-free at **Day 28**
- Mortality at **Day 21** and **Day 28**
- Number of days alive and free from invasive ventilation at **Day 21** and **Day 28**
- Number of days alive and free from non-invasive ventilation (NIV) at **Day 21** and **Day 28**
- Percentage of patients with improvement in severity status defined as a decrease in the severity score at **Day 28 or Discharge**, whichever comes first. Severity score will be defined as Mild, Moderate, Severe or Death based on PaO₂/FiO₂ ratio and patient status at Day 28 and numerically rated from 1-4 respectively:

Severity	Variable	Criteria
Mild - 1	PaO ₂ /FiO ₂ Ratio	200 mmHg < PaO ₂ /FIO ₂ ≤ 300 mmHg
Moderate - 2	PaO ₂ /FiO ₂ Ratio	100 mmHg < PaO ₂ /FIO ₂ ≤ 200 mmHg
Severe - 3	PaO ₂ /FiO ₂	Ratio PaO ₂ /FIO ₂ ≤ 100 mmHg
Death - 4	Patient Status	Yes/No

- Change from baseline in PaO₂/FiO₂ ratio at **6 and 12 hours following administration of each dose** in the treated group and at the similar timepoints in the control group (6, 12, 30, 36, 54 and 60 hours after randomisation)

Clinical Study Code No.: CLI-050000-04	Version No.: 4.0
EUDRACT No.: 2020-002632-75 – IND No: 153286	Date: 02 MAR 2021

- Change from baseline in PaO₂/FiO₂ ratio at additional timepoints (i.e. every 24 hours after treatment/randomisation until the patient is discharged from the ICU)
- Percentage of patients alive and with PaO₂/FiO₂ improvement of >20% at **6 and 12 hours following administration of each dose** in the treated group and at similar timepoints in the control group (6, 12, 30, 36, 54 and 60 hours after randomisation)
- Percentage of patients alive and with PaO₂/FiO₂ improvement of >20% at the additional timepoints (i.e. every 24 hours after treatment/randomisation till the patient is discharged from the ICU)
- Change from baseline in FiO₂ at **6 and 12 hours following administration of each dose** in the treated group and at similar timepoints in the control group (6, 12, 30, 36, 54 and 60 hours after randomisation)
- Change from baseline in FiO₂ at additional timepoints (i.e. every 24 hours after treatment/randomisation until the patient is discharged from the ICU)
- Length of ICU stay (days) **at Day 28**. Patients who die or are mechanically ventilated longer than this period are assigned with 28 days
- Percentage of patients alive and out of ICU **at Day 28**
- Delta SOFA Score and sub-score component measured on **Day 3 and Day 28 or Discharge** whichever comes first
- Percentage of patients alive and organ failure free (SOFA score=0) **at Day 28 or Discharge** whichever comes first
- Change from baseline in ventilatory parameters [tidal volume (TV), respiratory rate (RR), dynamic compliance (C_{dyn}), static compliance (C_{stat}), positive end-expiratory pressure (PEEP), peak inspiratory pressure (PIP), plateau pressure (P_{plat})] measured at 6-12-24h after each poractant alfa administration up to 72 hours and at similar timepoints in the control group (6, 12, 24, 30, 36, 48, 54, 60 and 72 hours after randomisation) and then every 24 hours till the patient is discharged from the ICU
- Change from baseline in blood gas analysis acid-base balance parameters (i.e. pH, pCO₂, pO₂, HCO₃, lactate) measured at 6-12-24h after each poractant alfa administration up to 72 hours and at similar timepoints in the control group (6, 12, 24, 30, 36, 48, 54, 60 and 72 hours after randomisation) and then every 24 hours till the patient is discharged from the ICU

Exploratory endpoints

The following parameters will be measured only on UK patients at 12, 24, 48, 72 and 96 hrs after start of treatment (first dose in the poractant alfa group) or after randomisation (in the control group):

- Change from baseline in lowest and dynamic surface tensions (mN/m) from TA samples
- Change from baseline in concentrations of surfactant phospholipids (mg/ml) and proteins (ng/ml) from TA samples
- Change from baseline in inflammatory indices such as cellular and cytokine (pg/ml) inflammatory markers (e.g. IL-1, IL-6, TNF alpha, IFN gamma and lymphocyte markers) from TA and blood samples

Clinical Study Code No.: CLI-050000-04	Version No.: 4.0
EUDRACT No.: 2020-002632-75 – IND No: 153286	Date: 02 MAR 2021

9. SAFETY ASSESSMENTS

- Adverse events (AEs)
- Laboratory Parameters (Blood count, bilirubin, creatinine, LDH, D-dimer, PRC, procalcitonin)
- Vital Signs (Blood pressures and heart rate)

10. ADVERSE EVENT REPORTING

10.1 Definitions

An **Adverse Event** is “any untoward medical occurrence in a patient or clinical trial patient administered a medicinal product and which does not necessarily have a causal relationship with this treatment”.

An adverse event can therefore be any unfavourable and unintended sign (including abnormal laboratory finding), symptom, or disease temporally associated with the use of a medicinal product, whether or not considered related to the medicinal product.

An **Adverse Drug Reaction** is an “untoward and unintended responses to an investigational medicinal product related to any dose administered”.

All adverse events judged by either the reporting Investigator or the Sponsor as having a reasonable causal relationship to a medicinal product qualify as adverse reactions. The expression “reasonable causal relationship” means to convey in general that there are facts (evidence) or arguments meant to suggest a causal relationship.

The definition covers also medication errors and uses outside what is foreseen in the protocol, including misuse and abuse of the product.

A **Serious Adverse Event (SAE)/Serious Adverse Drug Reaction** is any untoward medical occurrence or effect that at any dose falls in one or more of the following categories:

- **Results in death**

Death is not an adverse event but an outcome. It is the cause of death that should be considered if it is regarded as the adverse event. The only exception to this rule is “sudden death” where no cause has been established; in this latter instance, “sudden death” should be regarded as the adverse event and “fatal” as its reason for being serious.

- **Is life-threatening**

Life-threatening refers to an event in which the patient was at risk of death at the time of the event. The term does not refer to an event which hypothetically might have caused death if it were more severe.

- **Requires hospitalisation or prolongation of existing hospitalisation**

Hospitalization refers to a situation whereby an AE is associated with unplanned formal overnight admission into hospital, usually for purpose of investigating and/or treating the AE. Hospitalization for the treatment of a medical condition that occurs on an “elective” or “scheduled” basis or for a pre-existing condition that did not worsen during the study should not necessarily be regarded as an AE. Complications that occur during the hospitalisation are AEs. If a complication prolongs hospitalisation, the event is an SAE. Emergency room visits that do not result in a formal admission into hospital should be evaluated for one of the other seriousness criteria (e.g., life-threatening; persistent or significant disability or incapacity; medically significant).

Clinical Study Code No.: CLI-050000-04	Version No.: 4.0
EUDRACT No.: 2020-002632-75 – IND No: 153286	Date: 02 MAR 2021

As the enrolled patients will already be hospitalized at inclusion and during the first weeks of the study the above definition relating to hospital admissions and emergency room attendance will not be relevant during that inpatient period.

- **Results in persistent or significant disability or incapacity**

The term significant disability should be viewed as any situation whereby an AE has a clinically important effect on the patient's physical or psychological well-being to the extent that the patient is unable to function normally.

- **Is a congenital anomaly or birth defect**

- **Is a medically significant adverse event**

This criterion allows for any situations in which important adverse events/reactions that are not immediately life-threatening or do not result in death or hospitalisation may jeopardise the patient's health or may require intervention to prevent one of the above outcomes.

Examples of such events are: intensive treatment in an emergency room or at home for allergic bronchospasm; blood dyscrasias or convulsions that do not result in hospitalisation; or development of drug dependency or drug abuse.

Medical and scientific judgment should be exercised in deciding whether an event is serious because and medically significant.

Any suspected transmission via a medicinal product of an infectious agent is also considered a serious adverse reaction.

A **Non-Serious Adverse Event/Non-Serious Adverse Drug Reaction** is an adverse event or adverse drug reaction that does not meet the criteria listed above for a serious adverse event/serious adverse drug reaction.

10.2 Expectedness

An expected adverse reaction is an adverse reaction, the nature or severity of which is consistent with the applicable reference safety information (included in section 6.3.1.1 of the Curosurf[®] Investigator's Brochure), otherwise it is considered unexpected.

Reports which add significant information on specificity or severity of a known, already documented serious adverse drug reaction constitute unexpected events. For example, an event more specific or more severe than described in the Reference Safety Information would be considered as "unexpected". Examples of such events are: (a) acute renal failure as a labelled ADR with a subsequent new report of interstitial nephritis and (b) hepatitis with a first report of fulminant hepatitis.

10.3 Intensity of Adverse Event

Each Adverse Event must be rated on a 3-point scale of increasing intensity:

- **Mild:** The event causes a minor discomfort or patient does not lead to either modification of test treatment dosage or establishment of a correcting treatment
- **Moderate:** The event leads to a temporary interruption of the test treatment administration or to the establishment of a correcting treatment (local or non-invasive)
- **Severe:** The event causes severe discomfort. It may be of such severity to cause the definitive interruption of test treatment and invasive treatment

Clinical Study Code No.: CLI-050000-04	Version No.: 4.0
EUDRACT No.: 2020-002632-75 – IND No: 153286	Date: 02 MAR 2021

10.4 **Causality Assessment**

The following “binary” decision choice will be used by the Investigator to describe the causality assessment:

- Reasonable possibility of a relatedness
- No reasonable possibility of relatedness

The expression “reasonable possibility of relatedness” is meant to convey, in general, that there are facts (evidence) or arguments meant to suggest a causal relationship.

The Investigator will be asked to consider the following before reaching a decision on causality assessment:

- Time relationship between study drug intake and event’s onset
- Dechallenge (did the event abate after stopping drug?)
- Rechallenge (did the event reappear after reintroduction?)
- Medical history
- Study treatment(s)
- Mechanism of action of the study drug
- Class effects
- Other treatments-concomitant or previous
- Withdrawal of study treatment(s)
- Lack of efficacy/worsening of existing condition
- Erroneous treatment with study medication (or concomitant)
- Protocol related process

It should be emphasized that ineffective treatment should not be considered as causally related in the context of AE reporting.

10.5 **Action taken with the study drug due to an AE**

- Dose not changed
- Drug permanently withdrawn
- Not applicable

10.6 **Other actions taken**

- Specific therapy/Medication
- Concomitant Procedure

10.7 **Outcome**

Each Adverse Event must be rated by choosing among:

- Recovered/resolved
- Recovering/resolving

Clinical Study Code No.: CLI-050000-04	Version No.: 4.0
EUDRACT No.: 2020-002632-75 – IND No: 153286	Date: 02 MAR 2021

- Not recovered/not resolved
- Recovered with sequelae/resolved with sequelae
- Fatal
- Unknown

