10.2 Adverse Events

An adverse event (AE) will be classified as follow:

- For poractant alfa group:
 - Pre-treatment AE: if it starts before the first study medication administration (AE onset date/time < date/time of first study medication administration);
 - Treatment emergent AE (TEAE): if it starts on or after the first dose of study medication administration (AE onset date/time \geq date/time of first study medication administration).
- For control group:
 - Pre-treatment AE: if it starts before the randomisation date (AE onset date/time < start date/time of randomisation);
 - Treatment emergent AE (TEAE): if it starts on or after the randomization date (AE onset date/time \geq start date/time of randomisation).

An adverse drug reaction (ADR) is an AE related to study medication. A serious ADR is a serious AE (SAE) related to study medication.

A severe AE is an AE with severe intensity. Refer to Section 7.3 for missing severity.

An AE leading to discontinuation is an AE with action taken with study drug equal to “Drug Permanently Withdrawn”.

An AE leading to death is an AE with outcome equal to “Fatal”.

Pre-treatment AEs, and TEAEs will be presented separately. Pre-treatment AEs will be presented in the listings only.

Two AEs with the same PT and classified in the same category (pre-treatment AE or TEAE) will be considered as two different events when calculating the “number of events” in the tables.

A summary table displaying the number and the percentage of subjects experiencing at least one TEAE, serious TEAEs, non-serious TEAEs, ADRs/drug-related TEAE, serious ADRs, severe TEAEs, TEAEs leading to study drug discontinuation and TEAEs leading to death, as well as the number of events, will be presented by treatment group.

The SOC and PT will also be used for tabulation using the MedDRA dictionary. The number and percentage of subjects with at least one AE and the number of events will be presented by SOC and PT by treatment group for treatment emergent AEs, non-serious TEAEs, serious TEAEs, ADRs, serious ADRs, severe TEAEs, TEAEs leading to treatment discontinuation and TEAEs leading to death.

A table presenting the number and percentage of subjects with at least one TEAE will be provided by PT. The number of subjects with TEAEs will be also displayed by SOC and PT and maximum severity. The number of events will be also included in these analyses.

Tables will be presented by SOC and then by PT, alphabetically sorted.

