Table Number	Table Title	Template Code	Notes	Footnotes/Source Listing Number
Table 14.3.2.7	Serious Treatment Emergent Adverse Drug Reactions by System Organ Class and Preferred Term (Safety Set)	AET003	Display '-' in the first row for control group as this is not applicable.	Add the footnote: [1] System Organ Class and Preferred Term are coded using MedDRA Version 23.0. Source: Listing 16.2.7.6
Table 14.3.2.8	Severe Treatment Emergent Adverse Events by System Organ Class and Preferred Term (Safety Set)	AET003		Add the footnote: [1] System Organ Class and Preferred Term are coded using MedDRA Version 23.0. Source: Listing 16.2.7.7
Table 14.3.2.9	Treatment Emergent Adverse Events Leading to Study Drug Discontinuation by System Organ Class and Preferred Term (Safety Set)	AET003	Display '-' in the first row for control group as this is not applicable.	Add the footnote: [1] System Organ Class and Preferred Term are coded using MedDRA Version 23.0. Source: Listing 16.2.7.8
Table 14.3.2.10	Treatment Emergent Adverse Events Leading to Death by System Organ Class and Preferred Term (Safety Set)	AET003		Add the footnote: [1] System Organ Class and Preferred Term are coded using MedDRA Version 23.0. Source: Listing 16.2.7.9
Table 14.3.4.1	Vital Signs: Summary of Actual Values and Change from Baseline (Safety Set)	VST001	
 - Replace 'Visit' by 'Timepoint'. See Section 13.2.1 for the list of timepoints to display. - Repeat summaries for each parameter (Pulse Rate, Systolic Blood Pressure, and Diastolic Blood Pressure). - Remove '95% CI for mean' category. 	Add the footnote: [1] Duplicated data reported twice at 2 different timepoints are reported at the first occurrence for post dose/post randomisation and at the last occurrence for pre dose/pre randomisation. Source: Listing 16.2.8.1

Table Number	Table Title	Template Code	Notes	Footnotes/Source Listing Number
Table 14.3.4.2	Haematology: Summary of Actual Values and Change from Baseline (Safety Set)	LBT001	
 - Replace 'Visit' by 'Timepoint'. See Section 13.2.1 for the list of timepoints to display. - Repeat summaries for each parameter on the 'Haematology' CRF page. - Remove '95% CI for mean' category. 
In case of original unit missing, do not display the value in the table.
	
Source: Listing 16.2.8.2
 
Add the footnote: [1] Value with original unit missing are not displayed.

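### Adverse event intensity is partly tied to changes in the test treatment, so some early events can be moderate on poractant alfa but only mild in a control, and dosing interruptions have no action code

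*Protocol*

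**What the plan says.** Protocol 10.3 sets a single scale: "Each Adverse Event must be rated on a 3-point scale of increasing intensity". It has no separate wording for controls.

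- **Mild** covers minor discomfort where neither the dosing of the study drug is altered nor any corrective therapy is started.
- **Moderate** is defined in these words: "The event leads to a temporary interruption of the test treatment administration or to the establishment of a correcting treatment (local or non-invasive").
- For the **severe** grade the section states: "The event causes severe discomfort. It may be of such severity to cause the definitive interruption of test treatment and invasive treatment".

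Protocol 10.5 offers three codes for action on the study drug: 'Dose not changed', "Drug permanently withdrawn" and 'Not applicable'.

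SAP 10.2 carries the grade straight through: "A severe AE is an AE with severe intensity". It plans severe TEAEs by treatment group (Table 14.3.2.8, and a row in Table 14.3.2.1) and a display by system organ class, preferred term and maximum severity. SAP 7.4 gives a missing-severity rule for that display. SAP 10.2 identifies adverse events leading to discontinuation only by the permanent-withdrawal code. Listing 16.2.5 has a column headed 'Administration Interrupted'.

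**The concern.** The control arm has no test treatment to modify, interrupt or stop (Protocol 3.1; SAP 2), and the trial is open label (Protocol 6.6). Where the grade depends on what was done with the drug, the same clinical event can receive a different grade by arm simply because the rule was followed. The part of the scale that applies to both arms, discomfort, is hard to judge in patients expected to be sedated and ventilated (Protocol 15). Graders may therefore lean on treatment consequences.

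Tolerability is in the study title. What is at stake is whether a by-arm difference in intensity, or its absence, reflects the events or the grading rule, and whether events that interrupt an instillation can be identified in the adverse event tables.

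**Working it through.** The plan gives no figure on intensity to reproduce, so the check is mainly a reading of the text.

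**Step 1. Which criteria can apply in each arm (Protocol 10.3)**

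| Grade | Criteria usable in both arms | Criterion usable only on poractant alfa |
|---|---|---|
| Mild | Minor discomfort; no correcting treatment | No change in test treatment dosage |
| Moderate | Correcting treatment (local or non-invasive) | Temporary interruption |
| Severe | Severe discomfort; invasive treatment as a possible feature | Definitive interruption as a possible feature |

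The two moderate criteria are joined by 'or', so the drug criterion is sufficient by itself. In the severe grade, drug interruption is introduced by 'may be', so it describes what can happen and is not a requirement.

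**Step 2. A test case.** Take a brief desaturation on Day 1 that resolves without correcting treatment.
- On poractant alfa, the second dose is postponed. If postponement counts as temporary interruption, the event is moderate.
- In a control, no correcting treatment was given and there is no dose to postpone, so the event can only be mild.

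**Step 3. Where the difference goes.** It crosses the mild/moderate boundary. It therefore changes the maximum-severity summary but cannot change Table 14.3.2.8, which counts severe events only.

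**Step 4. When the wording can operate.** Doses are given three times, 24 hours apart (Protocol 6.2.3), so first to third dose spans 2 × 24 = 48 h. Against 28 × 24 = 672 h, that is 48/672 = 7.1%. Counting whole dosing days, it is 3/28 = 10.7%. These are shares of time, not of events, and do not measure bias. Events may cluster early.

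**Step 5. What would be needed to affect the severe table.** Suppose, as an assumption only, that the true severe rate p is equal in both arms, and that a fraction q of the remaining poractant patients were called severe only because the drug was stopped. The false excess is (1 − p) × q.

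| p (assumed) | q = 0% | q = 5% | q = 10% | q = 20% |
|---|---|---|---|---|
| 20% | 0 | 4 | 8 | 16 points |
| 40% | 0 | 3 | 6 | 12 points |
| 60% | 0 | 2 | 4 | 8 points |

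Nothing in the documents indicates a value of q above zero.

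**Step 6. 10.3 against 10.5.** An event graded moderate because dosing was temporarily interrupted has no matching action code. 'Dose not changed' does not record the interruption, and permanent withdrawal is wrong if dosing resumes. SAP 10.2 tabulates only permanent withdrawal. Table 14.3.1 summarises the number of administrations and the diluted volume given, without a link to an adverse event.

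**The case against.** The strongest reply is that the scale mostly works in both arms. Discomfort and correcting treatment apply to everyone, and the drug wording is inactive in both arms for about 89% of days (25/28). Intensity is not among the AE summaries in Protocol 12.3.7; it enters only through the SAP, which is descriptive throughout. The maximum-severity display is described in SAP 10.2 but has no numbered entry in SAP 16.1. Serious TEAEs and TEAEs leading to death are already planned by arm. Interruptions are not lost, because Listing 16.2.5 shows them. SAP 12 also says the study closed early, so rewording the protocol cannot alter collected grades without re-review.

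Most of this stands and limits the point. It does not remove it: the drug criterion is sufficient for moderate, no rule covers controls, and the 10.3/10.5 mismatch is there however severe is read. The SAP itself recognises the issue elsewhere: the ADR and drug-discontinuation tables print a dash for controls as not applicable, while Table 14.3.2.8 has no such note.

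A reader might infer that a control event can never be severe, or that Table 14.3.2.8 is not comparable between arms. The documents do not support either. Severe opens with severe discomfort, which a control can meet, and the test case in the working never reaches that boundary.

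**Conclusion.** The point holds in a limited form. Following Protocol 10.3 as written can grade identical early events differently by arm at the mild/moderate boundary, and this carries into the maximum-severity summary. Table 14.3.2.8 is at most at risk of some differential grading. Separately, 10.3 and 10.5 do not agree, so an adverse event that interrupts or postpones an instillation cannot be coded as such.

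The size is unknown. Neither the planned 28 of 70 patients in the control arm nor the 7.1% to 10.7% of time should be read as a measure of bias, and the 0 to 16 point range is illustration only.

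The conclusion assumes that a postponed dose counts as temporary interruption, that the maximum-severity display is by arm like its neighbours in SAP 10.2, and that controls appear in the safety tables. The last needs saying because the Safety Set in SAP 6.1, read literally, covers treated patients only. That is a separate matter, and correcting it would leave this one in place.

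**What to change.** - **Protocol 10.3:** define intensity by clinical impact and the correcting intervention needed, in the same words for both arms and without reference to the test treatment.
- **Protocol 10.5 and eCRF:** reconcile with 10.3 by adding an action category for interrupted or postponed administration. This concerns recording only, not when dosing should be interrupted.
- **SAP 10.2:** add one row for TEAEs with that action.

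If the data are already collected, three steps suffice:
1. Footnote the by-arm intensity summaries to say that the criteria refer to a treatment controls did not receive.
2. Tabulate the 'Administration Interrupted' data from Listing 16.2.5.
3. Rely on the planned serious-TEAE table (14.3.2.4) for the by-arm comparison, since the seriousness criteria in Protocol 10.1 do not depend on interrupting the test treatment.

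The cost is some protocol and eCRF wording, one action code and one table row. The downside is that events already graded need either re-review or the footnote.
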